Design Overview: This study will randomize 140 African American menthol cigarette smokers to receive either menthol cigarettes (i.e. continue smoking menthol cigarettes) or non-menthol cigarettes for a four week period. At the conclusion of the four week period, participants will attempt to quit smoking all cigarettes and will return for follow-up over a 6 month period. Tobacco use, nicotine use, motivation and self-efficacy to quit, nicotine craving and withdrawal measures and support for a ban on menthol cigarettes will be assessed during the study period. Urine cotinine concentrations will be measured at each visit. The primary outcome in this study is time from cessation to the first smoking lapse.

Subjects: In order to be eligible for this study, subjects must: 1) be African American (based on self-identification); 2) smoke primarily menthol cigarettes (greater than 80% of cigarettes smoked are menthol); 3) be between the ages of 18 and 64; 4) Smoke on average, at least 8 cigarettes per day for a period longer than 1 year and 5) express an interest in quitting smoking (rate themselves ≥ 7 on a 10 point scale assessing motivation to quit smoking). Subjects will be excluded if they have: 1) A current unstable medical / psychiatric condition as determined by self-report; 2) Substance abuse within six months of beginning the study based on self-report; 3) Regularly use any form of nicotine or tobacco other than cigarettes or 4) Are pregnant or breast feeding based on self-report (subjects will

be given a urine pregnancy test at the screening visit with pregnancy later in the study and breast feeding based on self-report).

As the risks associated with the study procedures are small, all medical assessments are based on self-report (except for a urine pregnancy test at screening).

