Recruitment will be limited to African American smokers for several reasons. Menthol cigarette use is particularly prevalent in the African American community with 80% of African Americans reporting menthol cigarettes as their usual choice (2). Additionally, data suggest that greater difficulty in cessation of menthol cigarettes (vs. non-menthol cigarettes) may be limited to African Americans (2) and therefore methods to improve cessation rates from menthol cigarettes are particularly relevant to this population. Since our preliminary study suggests that few menthol smokers spontaneously attempt to quit when asked to abstain from menthol cigarettes, we will only enroll those interested in smoking cessation.

African American menthol smokers will be recruited via the use of flyers and advertisements in local newspapers and neighborhood newspapers with a high African American readership or on internet resources such as Craigslist. If additional advertisement becomes necessary, radio or television advertisements may be utilized. Our research team has considerable experience recruiting smokers and we have determined which advertisement strategies are most effective.

Implementation Plan

Overview: Each subject will attend a screening visit to determine if they are eligible for the study. If subjects are eligible, they will be randomized to either the 'menthol' or 'non-menthol' group. Subjects will continue smoking in their normal manner for one week after the screening visit to gather information on their baseline smoking patterns after which they will attend a baseline visit. Week 0 will be considered their quit date, therefore the baseline visit will be week -4 (i.e. 4 weeks before their target quit date). Additional visits will be scheduled at week -3, week -2 and week 0 (i.e. 1, 2 and 4 weeks subsequent to the baseline visit). Follow up visits will occur at weeks 1, 2, 4, 6, 8, 12 and 26. The procedures occurring during each of these visits are described below.

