Screening Visit: All subjects will undergo a screening visit prior to enrollment at which written informed consent will be obtained and eligibility will be verified. Medical and psychiatric history will be obtained via subject report. Baseline questionnaires assessing smoking history and nicotine dependence will be administered. Exhaled carbon monoxide (CO) will be measured to confirm that they are smokers (CO \geq 8 ppm) with a NicCheck performed (with a cut-off of ≥ 5) for those who state that they smoke \geq 8 cigarettes per day but for whom CO is less than 8 ppm (e.g. they didn't smoke that morning, they are coming from a smoke free work environment, etc.). Subjects that qualify and are interested in participating will be asked to maintain a smoking diary for the duration of the study and will be scheduled for the baseline visit.

Baseline and Pre-Quit Visits: Smoking behavior subsequent to the screening visit will be determined as will subjects' level of craving, withdrawal, perceived health risk, motivation and self-efficacy to quit smoking and support for a menthol ban. At the baseline visit subjects will be told their randomization and given appropriate product (i.e. menthol or non-menthol cigarettes, based on randomization) at no cost to them for a total of 4 weeks. Subjects will be given a quantity of cigarettes equivalent to approximately 120% of their average daily use based on smoking diaries collected at the baseline visit or at pre-quit visits up to a maximum of approximately 1.5 packs per day. Since cigarettes packs generally contain 20 cigarettes, these percentages are approximations subject to rounding. This amount is chosen in case smoking increases as a result of switching to non- menthol and to allow for flexibility in scheduling subjects for subsequent visits (i.e. if a visit is delayed by several days, subjects will still have product). Subjects will be asked to smoke only study product for the 4 week period following the baseline visit. They will be given no specific instructions regarding using medicinal nicotine (i.e. nicotine patch, gum) or the use of e-cigarettes but will be asked to record any instances

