of using any nicotine or tobacco product. If subjects ask specifically about e-cigarettes, they will be told they can be used as long as they report their use at the next visit. Since e-cigarettes would be available to smokers were menthol cigarettes to be banned, to most closely mimic naturalistic conditions we will not ask subjects to abstain from e-cigarettes. However, since the risks of e-cigarette use are unclear as are their impact on cigarette cessation, we will also not encourage their use. In order to approximate what would likely occur were a menthol ban to be enacted, no specific instructions will be given to subjects about how to effectively quit but subjects will be encouraged to call the Smoking Quitline to obtain support for their cessation attempt. At each visit, exhaled carbon monoxide concentrations will be measured and subjects will complete questionnaires assessing craving and withdrawal symptoms, smoking urges, perceived health risk, and motivation to quit smoking. Subjects will also complete a food diary to assess menthol intake from sources other than cigarettes. A questionnaire assessing level of support for a menthol ban will be assessed at baseline, the week 0 (i.e. their quit day) visit and post-quit visits. At the baseline visit subjects will set a quit date which will be the day of their week 0 visit (i.e. they are not to smoke after the visit). If subjects wish to quit smoking the next day, that will also be allowed. At each visit, subjects will return all unused study product. In order to encourage smokers to bring back all unused product, subject payment will increase by the market value of the brand of cigarettes that they received (i.e. currently about \$8 per pack for most brands) based on how much they return. Since subjects will be provided cigarettes during the first month, they will not receive additional compensation (although parking will be provided). Returned cigarettes may be provided to the same subject as part of their subsequent supply but will not be used for any other subjects.

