At all visits, subjects will be asked to provide a urine sample. The urine will be used to measure cotinine concentrations and may in the future also be used to measure other markers related to smoking menthol cigarettes (such as other nicotine metabolites, menthol concentrations, tobacco toxicants, etc.). Subjects will also be asked to bring in their smoking diary in which they are to record cigarettes smoked as well as any other tobacco or nicotine products used (including e-cigarettes).

Follow up visits: Starting at Week 0 (quit date); subjects will attend follow up visits at weeks 1, 2, 4, 6, 8, 12 and 26. At each of these visits subjects will be asked if they have smoked at all since their previous visit. Exhaled carbon monoxide (CO) will be measured with an exhaled CO less than 8 ppm and a urine cotinine concentration of less than 50 ng/ml confirming abstinence (16). Smoking diaries will be used to determine time to lapse (time from their quit attempt until any smoking occurs) and time to relapse (time from their quit attempt until the first day of seven consecutive days that a cigarette is smoked).

Subjects will be paid \$20 for the screening visit, \$30 for each of the 7 visits between week 0 and week 12 with a \$100 bonus if they complete all visits up to week 12 and have complied with study related procedures. We anticipate that it will be more difficult to retain subjects through the 6 month visit; therefore subjects will receive \$60 for that visit. Since it is imperative that subjects honestly report any smoking during the study (in order to calculate time to lapse), payment during the cessation phase will not be contingent on successful abstinence. Subjects that relapse and resume smoking during the study will still be eligible to continue in the study. However, subjects that fail to follow study procedures (e.g. provide urine samples, fill out questionnaires, etc.) will be removed from the study.

Data and Safety Monitoring Plan:

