Time to lapse: The primary outcome, time to lapse following the week 0 visit, will be evaluated using a two-sided log-rank test. Since drop-outs could be more likely to lapse, we will perform two tests: one censoring drop-outs at the time of their last visit, and one considering drop-outs as lapsed at the time of their last visit. Randomization of 140 subjects should balance the groups with respect to potential confounding factors, and therefore no adjustment for other factors is planned. The same procedure will be used for the secondary outcome of time to relapse.

Other outcomes: Several continuous outcomes will be measured at baseline and subsequent time points, such as motivation and self-efficacy to quit, support for a menthol ban, severity of craving, perceived health risk, urinary cotinine concentrations, and exhaled CO. We will first calculate the change in each subject's outcome from baseline to the week 26 visit, and compare the study groups using two-sided, two sample t-tests. This will provide a straightforward comparison of whether cessation of menthol use affects long-term nicotine use and perceptions. Second, we will use analysis of variance (ANOVA) with repeated measurements to further analyze trends over all visits in the study period, with group, time, and interaction effects. This would identify more precisely when particular changes took place, or if any group differences emerged around the quit attempt but diminished by the end of the study. Changes in tobacco product use within groups will be summarized qualitatively and by descriptive statistics such as proportions.

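### CO and cotinine are read at two visits before the assigned product can act, but the week 26 arm comparison is an unadjusted change from one of them; adjusting for both would be more precise

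*Combined protocol and SAP*

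**What the plan says.** The combined protocol and SAP schedules two readings of each marker before product use.

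- **CO.** Under Screening Visit: "Exhaled carbon monoxide (CO) will be measured to confirm that they are smokers", with a cut-off of 8 ppm and a NicCheck for self-reported smokers who fall below it. Under Baseline and Pre-Quit Visits: "At each visit, exhaled carbon monoxide concentrations will be measured".
- **Cotinine.** Under Design Overview: "Urine cotinine concentrations will be measured at each visit". The paragraph before Follow up visits agrees: "At all visits, subjects will be asked to provide a urine sample".
- **Timing of exposure.** Under Implementation Plan, Overview: "Subjects will continue smoking in their normal manner for one week after the screening visit". Under Baseline and Pre-Quit Visits: "At the baseline visit subjects will be told their randomization and given appropriate product". Study product is for the four weeks after that visit.
- **Outcome visit.** "Follow up visits will occur at weeks 1, 2, 4, 6, 8, 12 and 26". Baseline is week -4, so the week 26 reading comes 30 weeks after baseline and after the quit attempt.

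Data Analysis, Other outcomes, then takes the change in each subject's "outcome from baseline to the week 26 visit, and compare the study groups" by two-sided two-sample t-tests. No covariates are named for these tests, and the screening value has no role in them. A repeated-measures ANOVA over the study visits follows. The text does not say whether screening counts as one of those visits.

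**The concern.** A change score fixes the weight on the baseline value at one. If baseline and week 26 are only moderately correlated, that weight is too large, and part of the baseline variation is carried into the comparison instead of being removed. A quit attempt between the two visits makes a moderate correlation plausible. The plan also holds a second pre-product value of each marker and does not use it in this comparison.

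What is at stake is the width of the confidence interval for the arm difference in CO and cotinine at week 26. The plan presents this comparison as its direct evidence on long-term nicotine use. The documents expect retention to be harder at week 26, and the power section gives its 120 subjects for time to lapse, not for week 26. Precision that can be had without more subjects is therefore worth taking.

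**Working it through.** **The plan's own figure.** Power and Sample Size states 80% power for an effect of 0.6 SD in continuous outcomes. With 120 subjects (60 per arm) and two-sided alpha 0.05, power is Φ(0.6 × √(60/2) − 1.96) = Φ(1.326) = 90.8%, or 90.3% by the noncentral t. The stated 80% is conservative: it needs only 44 to 45 per arm. An alternative reading that gives 80% takes 0.6 in SDs of the raw outcome, with a baseline to week 26 correlation of about 0.31. Either way, the plan's figures show no power shortfall that this point would repair.

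**Inputs.** The visit schedule is from the documents. The rest is assumed, because no SD or correlation is given for either marker: equal SDs (set to 1) at all three visits, r = screening-baseline correlation, and rho = correlation of either pre-product reading with week 26. The early readings are one week apart under unchanged smoking and the outcome is 30 weeks later, so r probably exceeds rho.

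**Variances of the arm comparison, per subject.**

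- Planned change score: 2(1 − rho)
- Change from the mean of the two readings: 1 + (1 + r)/2 − 2rho, a cut of (1 − r)/(4(1 − rho))
- Linear model, baseline only as covariate: 1 − rho²
- Linear model, both readings as covariates: 1 − 2rho²/(1 + r)

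| r, rho | Planned change | Change from mean of two (cut) | Model, baseline only | Model, both (cut vs planned) | Added by second reading |
|---|---|---|---|---|---|
| 0.9, 0.5 | 1.00 | 0.95 (5.0%) | 0.75 | 0.737 (26%) | 1.8% |
| 0.8, 0.5 | 1.00 | 0.90 (10.0%) | 0.75 | 0.722 (28%) | 3.7% |
| 0.8, 0.3 | 1.40 | 1.30 (7.1%) | 0.91 | 0.900 (36%) | 1.1% |
| 0.9, 0.3 | 1.40 | 1.35 (3.6%) | 0.91 | 0.905 (35%) | 0.5% |
| 0.5, 0.5 | 1.00 | 0.75 (25.0%) | 0.75 | 0.667 (33%) | 11.1% |

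Example, second row: 1 − 2(0.25)/1.8 = 0.722 against 2(0.5) = 1.00. The last column compares the two models: 1 − 0.722/0.75 = 3.7%.

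**Interval width.** A cut of 26% to 36% narrows the interval by 1 − √0.737 = 14% to 1 − √0.643 = 20%.

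**Where the gain comes from.** Adjusting for baseline alone cuts variance by (1 − rho)/2: 25% at rho = 0.5 and 35% at rho = 0.3. At rho = 0.7 it would be 15%.

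**Unequal SDs.** If the week 26 SD is k times the baseline SD, the change score has variance k² + 1 − 2k·rho and the baseline-only model k²(1 − rho²). The difference is (1 − k·rho)², which is never negative. Apart from degrees of freedom, the model cannot do worse.

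**Averaging can fail.** Suppose screening correlates 0.3 with week 26 and baseline 0.4. The planned variance is 2 − 0.8 = 1.20. Averaging gives 1 + 0.90 − 0.70 = 1.20 at r = 0.8 (no gain) and 1 + 0.95 − 0.70 = 1.25 at r = 0.9 (4.2% worse). The model estimates the two weights and avoids this.

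**The case against.** Measuring change from the visit at which product is handed out is conventional, simple and unbiased under randomisation. Only two of the listed secondary outcomes are involved, and on the plan's own inputs power is about 90%. The repeated-measures analysis may already include screening. All of this stands, and it keeps the point small.

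Screening CO is also an eligibility reading, so it tends to be selected high. That matters for within-arm falls, which would look larger if measured from it. It does not bias the arm comparison, because allocation is disclosed and product given only afterwards and both arms are selected alike. The order of measurement and handover at the baseline visit is not stated, but study product is for use after that visit.

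A reader might infer that averaging the two readings cuts the change-score variance by 25% at no cost, equivalent to going from 60 to 80 per arm. The documents do not support that. The figure requires one variance and one correlation across all three visits. The documents give neither, and a one-week gap before quitting set against a 30-week gap after it makes a common correlation unlikely. Under the assumed r of 0.8 to 0.9 and rho of 0.3 to 0.5, averaging gives about 4% to 10%, and it can give nothing.

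**Conclusion.** The point holds as an efficiency refinement. The planned week 26 comparison of CO and cotinine ignores one of two available pre-product readings and, more importantly, makes no covariate adjustment. With equal SDs and the (r, rho) pairs (0.9, 0.5), (0.8, 0.5) and (0.8, 0.3), modelling week 26 on arm and both readings cuts variance by about 26% to 36%. The unused screening value is the minor part: about 1% to 4% at r = 0.8, and 11% if r = rho = 0.5. These figures rest on assumed correlations and would be smaller if week 26 tracked the early readings closely.

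It should not be read as a finding of bias or of inadequate power. The primary log-rank analysis is untouched.

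**What to change.** In Data Analysis, Other outcomes, for CO and cotinine only, replace the between-arm change-score t-test with a linear model (ANCOVA) of the week 26 value on arm, with the screening and baseline values as covariates on the same scale as the outcome. If one pre-product value is missing, use the one available. Keep the baseline visit alone as the reference for within-arm descriptions. State whether screening enters the repeated-measures ANOVA. Settle this wording before outcome data are compared by arm.

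The cost is SAP text, with no new visit, sample or assay beyond those planned. Two covariates use two residual degrees of freedom, from 118 to 116 with 120 subjects. The adjusted arm difference will not exactly equal the difference between the reported within-arm changes, and a table footnote should say so.

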Power and Sample Size: Our primary outcome is time to lapse. Previous studies have found that during a cessation attempt most participants lapse within one week, at a median of 2-3 days after their quit attempt (35, 36). We plan on enrolling 140 subjects randomized 1:1 with an approximately 15% post-randomization visit dropout rate, leaving 120 subjects with data on time to lapse. This gives us over 80% power to detect a 1.7-fold difference using a significance cutoff of 0.05. We believe that such a difference would be a meaningful indicator of smoking success. The 1.7 fold difference in time to lapse is substantially smaller than is typically seen with medication studies. For example, an analysis by Shiffman et al (J Consult Clin Psychol 2006;74:276-85) found that the median duration of abstinence (i.e. time to lapse) was 6 days for active nicotine patch and 2 days for placebo. That would correspond to a 3 fold difference. Directly comparable data for other interventions is not available, however in a study comparing placebo to five different pharmacotherapy options (i.e. bupropion, nicotine lozenge, patch, bupropion + lozenge, patch + lozenge), the time until 50% of participants in the placebo group lapsed was approximately 6 days whereas the time for all other groups (except for nicotine lozenge) the time until 50% of participants lapsed was over 20 days (Japuntich et al. J Consult Clin Psychol 2011;79:34-42), an over 3-fold difference. Likewise, we

would have 80% power to detect an effect size of 0.6 in continuous secondary outcomes (i.e. a difference in group means of 0.6 times the outcome's standard deviation). Since it is not clear what the smallest difference is that would be important to detect, we believe that this sample size will be able to detect a meaningful difference.

Data and Record Keeping:

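### The continuous secondary outcomes have no missing-data rule, and the repeated-measures ANOVA names no covariance or sphericity correction; a mixed model on all available data is a better and cheap choice

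*Combined protocol and SAP*

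**What the plan says.** Under Data Analysis, Other outcomes, the combined protocol and SAP plans two analyses for motivation, self-efficacy, support for a ban, craving, perceived health risk, urinary cotinine and exhaled CO.

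- First, change from baseline to week 26 is calculated for each subject, and the plan will "compare the study groups using two-sided, two sample t-tests".
- Second, "we will use analysis of variance (ANOVA) with repeated measurements to further analyze trends over all visits in the study period". The model terms are arm, visit time and their interaction. This step is meant to show when changes took place and whether group differences faded.

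The visits are set out in the Implementation Plan, Overview: "the baseline visit will be week -4"; "Additional visits will be scheduled at week -3, week -2 and week 0"; "Follow up visits will occur at weeks 1, 2, 4, 6, 8, 12 and 26". That makes 11 visits. Baseline and Pre-Quit Visits places the support-for-ban questionnaire at baseline, week 0 and the post-quit visits only, which makes 9.

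On missing data, the Time to lapse paragraph says that drop-outs could be more likely to lapse. It gives two rules, censoring at the last visit or counting as lapsed at the last visit, and extends them to time to relapse. The continuous outcomes get no rule. Power and Sample Size assumes "an approximately 15% post-randomization visit dropout rate". The Follow up visits text adds: "We anticipate that it will be more difficult to retain subjects through the 6 month visit". It also provides for removing subjects who do not follow study procedures.

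**The concern.** Repeated-measures ANOVA usually means the classical split-plot analysis. Run that way, it raises two problems here.

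**Missing data.** The classical analysis keeps only subjects with a value at every visit, so one missed visit removes the whole series. The t-test is less demanding but still needs a week 26 value. Cotinine and CO reflect smoking directly. If drop-outs lapse more often, as the plan itself suspects, both analyses describe a sample selected on something close to the outcome.

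**Sphericity.** The time and group-by-time tests are valid without correction only under sphericity: differences between any two visits must all have the same variance. Equal variances with equal correlations are sufficient for this but not necessary. Here the visits are 1 to 14 weeks apart and straddle a quit attempt, so sphericity is doubtful. When it fails, the uncorrected interaction test rejects too often.

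The ANOVA is the only planned analysis that addresses the timing of group differences. It bears on the hypotheses about motivation, self-efficacy and support for a ban.

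**Working it through.** **The plan's own figure.** The documents give no size, covariance or complete-case count for the ANOVA. The nearest stated figure is 80% power for an effect of 0.6 SD in continuous secondary outcomes. With 120 subjects (60 per arm) and two-sided 5%, the two-sample t-test has 90.3% power, not 80%; 80% needs about 45 per arm. The statement is conservative. It would fit a loss of 1 − 45/70 = 36% by week 26, but the documents do not say this was meant. For the t-test, then, the main worry is who is missing rather than power.

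**Complete series under the classical ANOVA.** Inputs: 140 randomised and drop-out d = 0.15 (Power and Sample Size); 11 visits (Implementation Plan). The missed-visit rate m is an assumption, taken as independent across the 9 visits between baseline and week 26.

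Complete cases = 140 × (1 − d) × (1 − m)^9

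| m (assumed) | Fraction | Complete of 140 |
|---|---|---|
| 0 | 0.850 | 119 |
| 2% | 0.85 × 0.98^9 = 0.709 | 99 |
| 5% | 0.85 × 0.95^9 = 0.536 | 75 |
| 10% | 0.85 × 0.90^9 = 0.329 | 46 |

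If week 26 can also be missed at rate m (exponent 10), 1% leaves 108, 2% leaves 97 and 5% leaves 71. Standard errors scale as 1/√n, so 75 rather than 119 makes them √(119/75) = 1.26 times as large.

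**Size of the uncorrected group-by-time test.** Null data were simulated at the protocol's visit weeks: 60 per arm, complete series, 11 visits, F test on 10 and 1180 degrees of freedom, 4,000 to 20,000 trials per setting. Every covariance is an assumption. Where a setting was run more than once, the range is shown.

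| Assumed covariance | Size at nominal 5% |
|---|---|
| Equal variance and equal correlation | 4.3–5.2% |
| Exponential decay, 0.5 to 0.98 per week, no measurement error | 6.6–12.4% |
| Same decay, 30% measurement error | 5.7–7.2% |
| Decay, 20–30% error, 40% stable between-subject part | 5.2–7.0% |
| Pre/post-quit blocks, within/between correlation 0.5/0.4 | 5.3% |
| Blocks 0.6/0.4 | 6.6–7.1% |
| Blocks 0.7/0.3 | 10.2–10.7% |
| Blocks 0.8/0.2 | 12.0–13.2% |

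On the 9-visit schedule the decay settings give 5.1% to 11.5%.

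Box's approximation agrees: size ≈ P(F(10ε, 1180ε) > F critical value at 10, 1180), where ε measures the departure from sphericity. It gives 5.0% at ε = 1, 6.7% at 0.8, 10.3% at 0.5 and 12.0% at 0.4. The theoretical ceiling (ε = 1/10) is 17.8%.

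**After correction.** With Greenhouse-Geisser the size is 4.0% to 5.4% across the settings tried. A test with unstructured covariance gives 4.8% to 5.0% in the three decay settings where it was run.

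**The case against.** The strongest reply is that the plan is brief rather than wrong. It never says that incomplete subjects are excluded, that the F test is uncorrected or that correlations are equal. A mixed model with the same three terms, or a corrected F test, also fits its wording. This stands. A reader might infer that the plan requires complete data and discards participants; the documents do not say so, and the consequences above are conditional on the classical analysis.

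A reader might also infer a definite inflation, say 8% to 12% instead of 5%. The documents give no correlations, so no such figure can be derived. Ordinary measurement error or stable differences between subjects keep the size near 5% to 7% in the decay settings; values above 10% need strong serial correlation or a sharp break at the quit date.

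The sample-loss counts rest on assumed missed-visit rates, and the 15% is stated for time-to-lapse data rather than for week 26. The protocol also has retention measures: per-visit payment, a $100 bonus for completing visits to week 12, $60 for week 26, payment that does not depend on abstinence, and continued participation after relapse.

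Finally, a mixed model assumes missing at random, which is questionable if drop-out follows unobserved smoking. That also stands, and is why a sensitivity analysis belongs in the remedy.

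None of this supplies a missing-data rule for the continuous outcomes, or brings subjects without a week 26 value into the t-test.

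**Conclusion.** The point holds in conditional form. The plan names a repeated-measures ANOVA over up to 11 unevenly spaced visits (9 for support for a ban) and a t-test restricted to week 26 attenders, with no missing-data rule for either. Run classically, the ANOVA would use between 119 and 75 of 140 subjects at assumed missed-visit rates of 0 to 5%. Its uncorrected interaction test would have a size somewhere between about 5% and 13%. That upper end belongs to one assumed covariance and is not an estimate for this trial.

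The reach is limited. These are secondary outcomes and the ANOVA is the second step in their analysis. The sphericity problem does not touch the week 26 t-test, and neither problem touches the primary log-rank test, which has its own two drop-out rules. The change should be made because a clearly better method is available at little cost.

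**What to change.** Replace the ANOVA with a likelihood-based mixed model for repeated measures:

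- fixed effects for arm, visit (categorical), arm-by-visit, baseline value and baseline-by-visit;
- unstructured covariance, with a fallback stated in advance, such as heterogeneous variances with correlation decaying in actual weeks;
- Kenward-Roger degrees of freedom;
- every randomised subject with any post-baseline value included.

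Read the week 26 comparison and the other visit contrasts from this model, so that subjects lost before week 26 still contribute. Specify 9 visits for support for a ban. If an ANOVA F test is kept, apply the Greenhouse-Geisser correction.

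State the missing-at-random assumption and add one sensitivity analysis in which drop-outs are treated as having resumed smoking, for example with cotinine and CO set to the baseline value. This mirrors the second drop-out rule already used for time to lapse.

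The cost is a paragraph of SAP wording and standard software, with no new data collection. The downside is reliance on missing at random in the main model, which the sensitivity analysis probes but does not remove.
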